5.3.2 Part 3 Secondary Objectives

- To determine ORR by investigator assessment, duration of response (DOR), clinical benefit rate (CBR), duration of clinical benefit, disease control rate (DCR), duration of disease control, progression-free survival (PFS), time to progression (TTP), and overall survival (OS).
- To assess minimal residual disease (MRD) negativity in patients achieving CR.
- To further characterize safety and tolerability of modakafusp therapy.

- To collect PK data to evaluate population PK and exposure-response (safety/efficacy) analysis.
- To characterize the PK profile of modakafusp alfa in Chinese patients.
- To further characterize the immunogenicity of modakafusp alfa.
- To assess healthcare resource utilization.
- To evaluate patient-reported disease symptoms (includes bone aches or pain, back pain, hip pain, arm or shoulder pain, chest pain, and pain increasing with activity).

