- s. Antiplatelet antibodies will be collected and analyzed locally until the sponsor communicates to the sites that a sufficient number of samples have been obtained to stop the collection.
- ^t Coagulation panel (prothrombin time/international normalized ratio, activated partial thromboplastin time, fibrinogen, D-Dimer) to be performed if clinically significant bleeding occurs.

Appendix A Table 12 Part 3 Extension Schedule of Events: Screening, Baseline, Cycle 1, and Cycle 2											
Study Period	Screening	Treatment Phase – Cycle 1					Treatment Phase – Cycle 2				
Cycle Day		C1D1	C1D2	C1D8	C1D15	C1D22	C2D1	C2D2	C2D8	C2D15	C2D22
Window Allowed	≤21	0	0	±2 d	±2 d	±2 d	±2 d	±0 d	±2 d	±2 d	±2 d
Informed consent ^a	X										
Eligibility criteria	X										
Demographics	X										
Medical history	X										
Prior medication and treatment history	X										
Height and weight ^b	X						X				
ECOG performance status	X						X				
12-lead ECG °	X	X		X	X		X				
Physical examination (may be symptom-directed following screening visit)	Х	X		х			X				
Vital signs ^d	X	X		X	X	X	X		X	X	X
Monitoring of concomitant medication and procedures	Recorded from signing of the ICF through 30 days after last dose of study drug or start of subsequent anticancer therapy, whichever occurs first.										
AE reporting	Recorded from signing of the ICF through 30 days after last dose of study drug or start of subsequent anticancer therapy, whichever occurs first.										
	SAEs will be reported from signing of ICF through 30 days after last dose of study drug, even if the patient starts nonprotocol therapy.										
Dosing											
Modakafusp alfa infusion ^f		X					X				
Safety Laboratory Assessments											
Chemistry i (central analysis)	X	(X)		X	X	X	X		X	X	X
Hematology ^g (central analysis)	X	(X)		X	X	X	X		X	X	X
Thyroid function tests i (local analysis)	X										
Urinalysis k(local analysis)	X						X				
Pregnancy test ¹ (local analysis)	X	X					X				

Study Period	Screening		Traatma	nt Phas	e – Cycle	1		Treatmen	t Phase _	Cycle 2	
Cycle Day	Streening	C1D1			C1D15		C2D1	C2D2	C2D8	C2D15	C2D22
Window Allowed	<21	0	0	±2 d	±2 d	±2 d	±2 d	±0 d	±2 d	±2 d	±2 d
Serology ^j (local analysis)	(X)										
Coagulation panel * (local analysis)			To be	ındertak	en if clin	ically sign	ificant ble	eding is ob	served.	 	1
Disease Assessments											
Serum M-protein m, n (central analysis)	X	(X) n		Π			X		I	Ι	

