- A blood sample for quantification of Ig (IgM, IgG, and IgA) will be obtained. For the rare patient with known IgD or IgE MM, the quantitative test for that antibody will be followed at the same time points throughout the treatment period and PFS follow-up period as quantitative IgS (in addition to quantitative IgM, IgG, and IgA) (see Section 9.3.10.3). To be repeated at baseline (C1D1) if screening sample was taken more than 7 days before C1D1.
- For local analysis of disease assessment and cytogenetics at screening, a standard BMA drawn before consent is acceptable provided this is collected within 5 weeks of the first dose. All patients should also have a sample from screening sent for central cytogenetic analysis ("BMA for cytogenetics").
- u. Blood samples for PK will be collected at time points specified in Appendix C, Tables 9 and 10.
- v. All patients should have a fresh BMA sample from screening sent for central cytogenetic analysis.
- w. Predose.
- x. Coagulation panel (prothrombin time/international normalized ratio, activated partial thromboplastin time, fibrinogen, D-Dimer) to be performed if clinically

significant bleeding occurs.

- Blood samples for immunogenicity (ADA/NAb) testing will be collected before the dose on indicated visits during treatment and, if possible, at the EOT visit. In case of an infusion reaction, blood draws should be performed for central evaluation of immunogenicity (see Section 8.7.1.1). On days when dosing is not required, samples may be collected at any point during the clinic visit.
- ^{z.} Only repeat tests in parentheses for patients terminating treatment due to PD if they were not performed before for PD determination at the last visit, and for patients in CR if not performed before for CR confirmation.
- End-of-treatment laboratory assessments are to be performed prior to the patient starting a new treatment or a maximum of 30 days following the last dose.
- Patients will have PFS follow-up every 4 weeks from the EOT visit until the occurrence of PD, death, the start of subsequent systemic antineoplastic therapy, study termination, or until 6 months after the discontinuation of study treatment, whichever occurs first.
- cc. OS follow-up continues every 12 weeks until death, study termination, or patient withdrawal.
- dd. Predose and at 4 hours (\pm 60 minutes) after the end of infusion.

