Appendix C Table 9 Parts 1 and 2 Schedule D (Q4W) PK Sampling: Cycle 3 and Beyond

Time Points	Day 1 ^a	Day 2 ^b
Predose (within 30 min prior to start of infusion)	X	
End of infusion (±10 min)	X	
2 to 4 hours after end of infusion (±30 min)	X	
24 hours after the end of the infusion (±1 hr)		X

PK: pharmacokinetic; Q4W: every 4 weeks.

a. Mofakafusp alfa infusion. The timing of the morning visits should occur at approximately the same time as the morning infusion times on previous infusion visits.

b. Day 2 of Cycles 3, 7, and 11 only.

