Appendix C Table 10 Part 3 Extension PK Sampling: Cycles 1 and 2 a									
Cycle 1						Cycle 2			
Timepoints	Day 1	Day 2	Day 8	Day 15	Day 1	Day 2	Day 8	Day 15	
Predose (within 30 min prior to start of infusion)	X				X				
End of infusion (±10 min)	X				X				
2 to 4 hours after end of infusion (±30 min)	X				X				
During the clinic visit		X	X	X		X	X	X	

PK: pharmacokinetic.

^a Not applicable to patients enrolled in China with intensive PK schedule (Table 11), but applicable to all other patients enrolled in China.

Time Points	Day 1 into Day 2 a	Day 3	Day 8	Day 15	Day 22
Predose (within 30 min prior to start of infusion)	X				
End of infusion (±10 min)	X				
2 hours after end of infusion (±30 min)	X				
4 hours after end of infusion (±30 min)	X				
6 hours after end of infusion (±30 min)	X				
24 hours after end of infusion (±1 hour)	X				
48 hours after end of infusion (±1 hour)		X			
168 hours after end of infusion (±2 hour)			X		
336 hours after end of infusion (±4 hour)				X	
504 hours after end of infusion (± 4 hour)					X

PK: pharmacokinetics.

Note: Intensive PK samples will be collected only in up to 8 Chinese patients enrolled in China per dose upon laboratory kit availability.

The timing of the morning visits should occur at approximately the same time as the morning dosing on previous dosing visits.

^a Blood sample for Day 1 predose will be collected within 30 minutes before start of any drug administration.

	Cycle 3 and beyond					
Time Points	Day 1	Day 2 a	EOT			
Predose (within 30 min prior to start of infusion)	X					
End of infusion (±10 min)	X					
2 to 4 hours after end of infusion (±30 min)	X					
During the clinic visit		X	X			

PK: pharmacokinetic.

a. Day 2 of Cycles 5 and 11 only.

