		embryo-fetal lethality effects with modakafusp alfa, genotoxicity assessments are not required for biologics due to a lack of demonstrable interaction with DNA and accepted low risk from health authorities. Based on these considerations, modakafusp alfa is considered nongenotoxic and falls into the category of possible human teratogenicity/fetal toxicity based on a lack of data. United States (US) Food and Drug Administration (FDA) guidelines for nongenotoxic biologic pharmaceuticals with a potential for teratogenicity or embryo-fetal lethality recommend a contraception period of 5 half-lives after the last dose for females and no additional duration after the last dose for males. The half-life of modakafusp alfa is less than 24 hours. Similarly, for therapeutics with these characteristics, the Clinical Trial Facilitation Group (CTFG) recommends contraception in females for the duration of systemic exposure plus 1 month and no contraception requirements in males for biologics is due to a low likelihood of exposure to childbearing partners (lack of semen accumulation, limited absorption, and likely proteolytic degradation by vaginal/cervical enzymes) (Scialli et al. 2015). Based on the current lack of reproductive toxicity data with modakafusp alfa, the duration of contraception was extended over that recommended by guidance	toxicity testing. In accordance with regulatory guidelines (ICH Guidances S6(R1) 2011, and S9, 2009), a weight-of-evidence approach is used to assess the risk of reproductive toxicity of modakafusp alfa. While there are no direct nonclinical data to support a lack of teratogenicity or embryofetal lethality effects with modakafusp alfa, genotoxicity assessments are not required for biologics due to a lack of demonstrable interaction with DNA and accepted low risk from health authorities. Based on these considerations, modakafusp alfa is considered nongenotoxic and falls into the category of possible human teratogenicity/fetal toxicity based on a lack of data. United States (US) Food and Drug Administration (FDA) guidelines for nongenotoxic biologic pharmaceuticals with a potential for teratogenicity or embryo-fetal lethality recommend a contraception period of 5 half-lives after the last dose for females and no additional duration after the last dose for males. The half-life of modakafusp alfa is less than 24 hours. Similarly, for therapeutics with these characteristics, the Clinical Trial Facilitation Group (CTFG) recommends contraception in females for the duration of systemic exposure plus 1 month and no contraception in males. The lack of contraception requirements in males for biologics is due to a low likelihood of exposure to childbearing partners (lack of semen accumulation, limited absorption, and likely proteolytic degradation by vaginal/cervical enzymes) (Scialli et al. 2015). Based on the current lack of reproductive toxicity data with modakafusp alfa, the duration of contraception was extended over that recommended by guidance from the FDA and the CTFG. The duration of contraception after the last dose of modakafusp alfa of 6 months after the last dose for females and 120 days after the last dose for females and 120 days after the last		

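### The Part 3 schedule of events disagrees with Appendix C Table 11, so the 48 h and 504 h intensive-PK samples in Chinese patients are at risk of being missed

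*Protocol*

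**What the plan says.** **The objective.** Protocol Section 5.3.2 lists as a Part 3 secondary objective "To characterize the PK profile of modakafusp alfa in Chinese patients". Section 5.4.3.2 turns it into an endpoint: summary statistics for Cmax, AUC∞, AUClast, λz, tmax, CL, Vss and t1/2z in the Chinese patients on the intensive schedule. SAP Sections 5.3.2 and 7.11.1.2 repeat this.

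**The sampling tables.** Appendix C has three Part 3 tables.
- Table 10 (Cycles 1 and 2) carries the footnote "Not applicable to patients enrolled in China with intensive PK schedule (Table 11), but applicable to all other patients enrolled in China".
- Table 11 is the intensive schedule for Cycles 1 and 2, in up to 8 Chinese patients per dose. It includes a 48 h sample on Day 3 and a 504 h sample on Day 22.
- Table 12 covers Cycle 3 onward, with an EOT sample and Day 2 samples restricted to "Day 2 of Cycles 5 and 11 only".

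**The schedule of events.** After screening, Appendix A Table 12 has the columns "C1D1 C1D2 C1D8 C1D15 C1D22 C2D1 C2D2 C2D8 C2D15 C2D22". Its PK row is marked on Days 1, 2, 8 and 15 of each cycle and is blank on Day 22. Footnote u to that row says "Blood samples for PK will be collected at time points specified in Appendix C, Tables 9 and 10". The Table 9 it cites is titled "Parts 1 and 2 Schedule D (Q4W) PK Sampling: Cycle 3 and Beyond".

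**The body text.** Section 9.3 refers to Appendices A, B and C for the timing of assessments, and Section 9.3.11.2 refers to Appendix C as a whole for PK times.

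**The concern.** The schedule of events is what a site normally uses to book visits and draw samples. Here it offers no visit for one of the intensive samples and no PK mark for another, and its footnote cites one table from the wrong study parts and one that excludes the patients concerned.

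The Chinese PK endpoint is estimated by noncompartmental methods in a small subset, so each profile depends on its late samples. A 48 h sample not taken cannot be recovered for that cycle.

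The wrong reference also touches Part 3 patients outside the subset. Appendix C Table 9 asks for Day 2 samples in Cycles 3, 7 and 11, whereas Appendix C Table 12 asks for them in Cycles 5 and 11. The Part 3 grid has C5D2 and C11D2 but no C3D2 or C7D2.

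**Working it through.** The plan states no figure to reproduce, so the check sets the tables side by side. Each Table 11 time is converted to a cycle day by day = 1 + hours/24, and that day is looked up in Appendix A Table 12.

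| Table 11 time | Cycle day | Visit column in Appendix A Table 12 | PK mark |
|---|---|---|---|
| Predose, end of infusion, 2 h, 4 h, 6 h | 1 | yes | yes |
| 24 h | 1 + 24/24 = 2 | yes | yes |
| 48 h | 1 + 48/24 = 3 | **no** | **no** |
| 168 h | 1 + 168/24 = 8 | yes | yes |
| 336 h | 1 + 336/24 = 15 | yes | yes |
| 504 h | 1 + 504/24 = 22 | yes | **no** |

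**Coverage.** Eight of ten time points per cycle fall on a day with a PK mark. One (48 h) has no visit, and one (504 h) has a visit but no mark. Over two cycles that is 2 × 2 = 4 of 20 samples per patient. With up to 8 patients at each of two doses, up to 8 × 2 × 2 = 32 of the 48 h samples have no scheduled visit.

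**If a site applied the cited Table 10 to these patients.** Table 10 has six samples per cycle: predose, end of infusion, one at 2 to 4 h, and Days 2, 8 and 15. Against ten in Table 11 the loss is 10 − 6 = 4 per cycle: the 2, 4 and 6 h samples become one, and 48 h and 504 h disappear.

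**Which loss matters.** After 24 h, Table 11 samples at 48, 168, 336 and 504 h. Without 48 h the gap runs from 24 to 168 h, or 144 h. The terminal slope λz then has no point in that gap. The other parameters follow from it: t1/2z = ln 2/λz, AUC∞ = AUClast + Clast/λz, and CL = dose/AUC∞, with Vss depending on CL. Cmax and tmax come from the Day 1 samples.

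**Does the SAP screen out thin profiles?** SAP Section 7.11.1.2 allows exclusion when AUC is judged unreliable because 50% or more of the data are missing. Missing two of ten is 20%, and missing four of ten is 40%. Neither reaches that level, so the parameters could be computed from the thinner profile.

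**Timing windows.** The schedule of events allows the Day 2 sample at any time that day (footnote o), against 24 h ±1 h in Table 11. It allows ±2 days (±48 h) on Days 8, 15 and 22, against ±2 h at 168 h and ±4 h at 336 h and 504 h.

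**Comparison within the protocol.** Parts 1 and 2 Schedule D uses the same 48 h and 504 h times (Appendix C Table 8). Its schedule of events (Appendix A Table 9) has C1D3 and C2D3 columns with PK marks, and footnoted PK marks on Day 22. Leaving such entries out of the grid is therefore not this protocol's convention.

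**The case against.** The strongest reply is that the protocol read as a whole does specify these samples. The Appendix A PK row gives no clock times, so a site must open Appendix C. Footnote u leads to Table 10, whose footnote a takes the intensive patients out and names Table 11. Sections 9.3 and 9.3.11.2 cite Appendix C without limiting the tables, and the study summary describes the intensive sampling. This stands. A reader might infer that the objective cannot be met by following the protocol; the documents do not support that. Cmax and tmax are also untouched, and Section 13.1.4 promises parameters only as the data permit.

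Three further inferences go too far.

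- **That the 504 h sample has no visit.** C1D22 and C2D22 are scheduled, with vital signs, chemistry and hematology. Only the PK mark is missing. The sample may also carry less weight: in Schedule D it was strongly recommended only above 6 mg/kg, and the Part 3 doses correspond to 1.5 and 3 mg/kg.
- **That Part 3 loses its EOT PK sample.** Appendix A Table 13 marks PK at EOT, C5D2 and C11D2, in agreement with Appendix C Table 12. Footnote u conflicts with those marks but does not remove them.
- **That the loss can be sized from the half-life.** Appendix J contains the sentence "The half-life of modakafusp alfa is less than 24 hours", but it is Czech country-specific text to an amendment listed as not harmonized with global Amendment 9. A single constant half-life also does not fit the nonlinear, target-mediated elimination described in Section 4.6.2.1.

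The wide visit windows are partly offset because SAP Section 7.11.1.2 uses actual sampling times. That helps a sample taken late, not one never taken.

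**Conclusion.** The concern holds as an internal inconsistency. Appendix A Table 12 has no Day 3 visit for the 48 h sample and no PK mark on Day 22 for the 504 h sample, and footnote u cites the wrong set of tables. The samples are at risk of being missed; they are not absent from the protocol.

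The effect is limited to a descriptive secondary endpoint in up to 8 patients per dose and does not reach the Part 3 primary endpoint. Within that endpoint, the exposure is mainly λz, t1/2z and AUC∞, and CL and Vss through them, and it comes chiefly from the 48 h sample. How many samples would be lost cannot be derived from the documents. It depends on how far sites work from the grid alone, and on the laboratory and operations manuals, which are not included.

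The likely cause, as an inference only, is stale numbering. The Amendment 9 log lists Appendix C but not Appendix A for the intensive-PK addition, and it records the insertion of a previously omitted Schedule D table.

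The correction should be made: an instruction to sites contradicts the sampling table on which a stated endpoint depends.

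**What to change.** 1. Change footnote u to cite Appendix C Tables 10, 11 and 12.
2. In Appendix A Table 12, add C1D3 and C2D3 columns with a PK mark, and add PK marks at C1D22 and C2D22, all limited by footnote to the China intensive-PK patients.
3. State that for those patients the Table 11 sampling windows govern, in place of footnote o's allowance for Day 2 and the ±2-day visit windows.

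The cost is protocol schedule wording. Table 11 already requires every one of these samples and, by implication, attendance on Day 3, so no procedure is added beyond it. The SAP parameter list and methods do not change.
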